Sample Size Calculation (This has NOT changed from original IRB): The sample sizes are calculated separately for the two risk groups (650 in surveillance group and 650 in screening group). Among the surveillance group, we want to test non-inferiority in sensitivity and superiority in specificity of LCE+HRME vs. LCE alone. The standard endoscopic evaluation using LCE has high sensitivity of about 95% but with low specificity at about 65%. Based on the preliminary data, we hypothesize that LCE+HRME has the sensitivity of at least 90% level, which is similar to that of LCE, but LCE+HRME would improve the specificity to 85%. With significance level of 0.05 and 80% power, we need 223 neoplastic patients and 65 benign patients in each arm (LCE and LCE+HRME) to conclude that LCE+HRME has similar sensitivity as LCE alone and had higher specificity than LCE alone. Hence, we need 446 neoplastic patients and 130 benign patients. The sample size calculation is based on the formula in Pepe (Chapter 8, The statistical Evaluation of Medical Tests for Classification and Prediction, 2003).

According to the preliminary results, greater than 80% patients in the surveillance group would have neoplasia. We anticipate the enrollment of total 650 patients in the surveillance group to ensure the accrual of 446 neoplastic patients and 130 benign patients.

In screening group, we will study the accuracy of LCE+HRME for the diagnosis of neoplasia, and test whether the negative predictive value (NPV) of LCE+HRME is higher than LCE alone. The NPV for using LCE alone is about 95%. We hypothesize that the NPV for LCE+HRME should be at least 99% to be useful. A sample of 300 per arm would provide 82.1% power for this hypothesis with a 5% type-I error. Assuming an 8% loss to follow-up or incomplete data, we need to recruit 325 subjects per arm in the screening population.

Power Calculation (Augmented Reality HRME Revision): We anticipate having at least 400-500 subjects remaining by the time the Augmented Reality HRME revision IRB is approved and funding from the NCI obtained. With 400 patient Augmented Reality HRME data, assuming an accuracy of 83% AND 650 LC patient, assuming an accuracy of 57%, the study should have >93% power to detect a statistically significant difference with an alpha error rate of 0.05.

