For the HRME image interpretation study, the sample size of 10 endoscopists was selected based on a prior power analysis based on non-inferiority. The 10 endoscopists will review about 140 HRME images. It is hypothesized that software interpretation of the HRME images will be non-inferior to the endoscopist interpretation. Non-inferiority is defined as a 10% difference in specificity between the two groups with 90% power and alpha of 0.05.

G2. Data Analysis

Provide a description of your plan for data analysis. State the types of comparisons you plan (e.g. comparison of means, comparison of proportions, regressions, analysis of variance). Which is the PRIMARY comparison/analysis? How will the analyses proposed relate to the primary purposes of your study?

Among the surveillance group, three analyses in testing the null hypotheses will be performed, including two interim analyses and one final analysis. The analysis will be performed when 220, 440 and 650 study subjects have been accrued, respectively.

The interim analysis will use a symmetric two sided group sequential design using a Hwang-Shih-DeCani spending function with beta spending of .4, which provides an O'Brien-Fleming-like conservative upper bound. This approach requires a two sided significance level of 0.0026 and 0.0114 for the interim analysis and 0.0464 for the final analysis of overall survival.

There will be no interim analysis for the screening population.

The primary analysis for the surveillance group is to test non-inferiority in sensitivity and superiority in specificity of LCE+HRME vs. LCE alone. The test statistic is based on the formula in Pepe (Chapter 8, The statistical Evaluation of Medical Tests for Classification and Prediction, 2003). Additionally, sensitivity and specificity of LCE+HRME vs. LCE alone will be estimated on a per patient basis with 95% confidence intervals. The primary goal for the screening group is to test whether the negative predictive value (NPV) of LCE+HRME is higher than LCE alone. This is done using Fisher's exact test. Additionally, the negative predictive value will be summarized with 95% confidence intervals.

The secondary analysis includes diagnostic yield, clinical efficiency, clinical impact, progression rate, and the rate of adverse events.

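### The 80% power stated for the surveillance group holds for each test alone at one-sided 0.05; power to conclude both is about 64–68%, and lower if the two-sided levels in G2 apply

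*Combined protocol and SAP*

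**What the plan says.** Section G1 (Sample Size Calculation) takes Lugol's chromoendoscopy alone (LCE) to have about 95% sensitivity and 65% specificity, and expects LCE+HRME to raise specificity to 85%. On sensitivity it says: "we hypothesize that LCE+HRME has the sensitivity of at least 90% level, which is similar to that of LCE". It then gives one alpha and one power: "With significance level of 0.05 and 80% power, we need 223 neoplastic patients and 65 benign patients in each arm". The purpose follows in the same sentence: "to conclude that LCE+HRME has similar sensitivity as LCE alone and had higher specificity than LCE alone". G1 does not say whether 0.05 is one-sided or two-sided, and it names no non-inferiority margin for this group.

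Enrolment is set at 650, because "greater than 80% patients in the surveillance group would have neoplasia".

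Section G2 says: "The primary analysis for the surveillance group is to test non-inferiority in sensitivity and superiority in specificity of LCE+HRME vs. LCE alone". It plans looks at 220, 440 and 650 subjects: "The interim analysis will use a symmetric two sided group sequential design". The levels are a "two sided significance level of 0.0026 and 0.0114 for the interim analysis and 0.0464 for the final analysis of overall survival".

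**The concern.** Two parts of the calculation do not fit together.

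First, one power figure is given for a conclusion that needs two tests to succeed. If each test was sized for 80% on its own, the chance that both succeed is well below 80%. G2 names the pair as the primary analysis, so joint power is the figure a reader needs.

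Second, G1 and G2 may use different significance levels. A two-sided final level of 0.0464 is 0.0232 in each direction, a much stricter standard than one-sided 0.05. The level is also tied to overall survival, which this trial does not measure as an endpoint. The documents therefore do not settle which level the primary tests must meet, and a result between the two levels would be open to dispute.

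**Working it through.** **Inputs.** From G1: LCE sensitivity 0.95; specificity 0.65 vs 0.85, so false-positive fractions 0.35 vs 0.15; alpha 0.05; power 80%; equal arms (446/2 = 223, 130/2 = 65). Inferred because they reproduce the plan's number: true sensitivity 0.95 in both arms, and 0.90 as the limit, so a null ratio of 0.90/0.95 = 0.947.

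**Step 1: reproduce 223 and 65.** For two independent arms on the log-ratio scale,

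n per arm = (z_α + z_β)² × [(1−pA)/pA + (1−pB)/pB] / [ln((pA/pB)/δ0)]².

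At one-sided 0.05 and 80% power, (1.645 + 0.842)² = 6.183.

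- Sensitivity: 6.183 × 0.10526 / (0.05407)² = 222.6, rounded up to 223.
- Specificity (false-positive fractions, δ0 = 1): 6.183 × 7.5238 / (0.8473)² = 64.8, rounded up to 65.

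Both match. The other conventions tried do not:

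| Convention | Neoplastic per arm | Benign per arm |
|---|---|---|
| Log ratio, one-sided 0.05 | 223 | 65 |
| Log ratio, two-sided 0.05 | 283 | 83 |
| Difference scale, one-sided 0.05 | 235 | 55 |
| Difference scale, two-sided 0.05 | 299 | 70 |
| Log ratio, one-sided 0.05, 80% joint power | 302 | 88 |

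The last row sets each test at √0.8 = 89.4% power.

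**Step 2: joint power at one-sided 0.05.** Sensitivity is tested in neoplastic patients and specificity in benign ones. The groups do not overlap, so for given group sizes the powers multiply.

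| Per arm (neoplastic/benign) | Sensitivity | Specificity | Joint | Joint, exact binomial |
|---|---|---|---|---|
| 223/65 | 0.801 | 0.801 | 64.1% | 67.2% |
| 260/65 (650 patients, 80% neoplasia) | 0.851 | 0.801 | 68.2% | 71.1% |
| 276/49 (650 patients, 85% neoplasia) | 0.869 | 0.698 | 60.6% | 64.1% |

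The exact column enumerates binomial outcomes for the same log-ratio Wald tests. The 85% is an assumption for illustration. The plan expects more than 80% neoplasia, and any figure above 80% leaves fewer than 65 benign patients per arm among 650.

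**Step 3: joint power if the G2 levels govern.** Each two-sided level is halved.

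- Final level alone (0.0232): 0.690 × 0.691 = 47.7% at 223/65; 0.757 × 0.691 = 52.3% at 260/65. Exact: 50.8% and 55.3%.
- Three looks at 220/440/650, with both groups accruing in proportion: 0.697 × 0.697 = 48.6% at 223/65; 0.762 × 0.697 = 53.1% at 260/65; 45.2% at 276/49.
- G2 levels for specificity only, one-sided 0.05 for sensitivity: about 55–56% at 223/65 and 59% at 260/65.

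**Step 4: can the level change the verdict?** Suppose LCE+HRME detects 209/223 (93.7%) and LCE 212/223 (95.1%).

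- Estimate: ln(209/212) − ln(0.90/0.95) = 0.0398.
- Standard error: 0.0231.
- Z = 1.724, one-sided p = 0.042.

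This is non-inferior at one-sided 0.05 but not at 0.0232.

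**Step 5: the unstated limit.** If 90% were the true LCE+HRME sensitivity and not the limit, the truth would sit on the null ratio and non-inferiority power would be 5%. The number 223 therefore works only if 90% is the limit.

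**The case against.** - **The 80% may be meant per test.** G1 does not call it a joint probability, and G2 states no explicit rule that both tests must succeed. On that reading 223 and 65 are correct, and the fault is that joint power is not disclosed. This is fair, but the sentence in G1 ties the figure to concluding both, and a reader would take it that way.
- **The normal approximation is slightly pessimistic.** Exact power of the same tests is 67–71%, so the shortfall is 9–13 points, against 12–16 by the plan's apparent formula. This stands. No version reaches 80%.
- **The inputs are inferred.** The formula is in a cited book and the plan does not list its inputs. This stands as a caveat. Still, one convention returning both integers is strong evidence, and the usual alternatives miss.
- **The lowest figures assume the G2 levels apply, and halve them for a directional test.** This stands, so those figures are conditional. That the plan does not settle the matter is itself the second half of the problem.
- **Enrolling 650 exceeds the 576 required (446 + 130).** The surplus helps only sensitivity. At 80% neoplasia the benign count is exactly 65 per arm, and above 80% it is lower.

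**Conclusion.** The concern holds. As written, the power is overstated for the conclusion it accompanies by 12 to 16 points on the plan's apparent formula, or 9 to 13 by exact calculation. This rests on equal 95% sensitivity, a 90% limit, one-sided 0.05 and both tests having to succeed. If 80% is read as per test, the error becomes an omission.

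The conflict of alpha between G1 and G2 does not depend on that reading. The sizes fit one-sided 0.05, while G2 describes two-sided levels attached to something that is not an endpoint. If those levels govern both tests, joint power is roughly one half. The randomised comparison itself is not in question.

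**What to change.** Four changes of wording, made before the data are analysed:

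1. **Power (G1).** State that each test has 80% power at one-sided 0.05, and that power to conclude both is about 64% with 223 neoplastic and 65 benign per arm, or about 68% with 260 neoplastic per arm. Name the method; the exact figures are 67% and 71%. If the G2 levels are meant to govern both tests, state about 48–53% instead (51–55% exact at the final level). Note that more than 80% neoplasia lowers the benign count below 65 per arm.
2. **Alpha (G1 and G2).** Use the same sidedness and level in both sections.
3. **Non-inferiority limit (G1).** If that was the intention, state that 90% sensitivity (ratio 0.947) is the limit and that power assumes 95% in both arms.
4. **Group sequential levels (G2).** Attach 0.0026, 0.0114 and 0.0464 to the sensitivity and specificity tests, remove the reference to overall survival, and say how two-sided levels apply to a directional non-inferiority test.

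The cost is a protocol and SAP edit and a less favourable power statement. The sample size and the primary comparison stay as they are. For reference, 80% joint power at one-sided 0.05 would need 302 and 88 per arm; that is not being asked for.

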Separately, 10 endoscopists (6 novice and 4 expert) will be asked to interpret a selection of the HRME images. The novices will include current GI fellows at BCM and novice endoscopists on the protocol, while the expert endoscopists will be experienced endoscopists listed on the protocol. The 10 subjects will receive information about the procedures verbally as a waiver of documentation of consent is requested. Each of the subjects will first receive training using a training set, and then will be evaluated using a testing set of images. They will be asked to give a read (neoplastic or non-neoplastic) and then to provide their confidence level (high or low) for each image determination. Following the subjective HRME image read, each image will be evaluated using the automated software algorithm, with the subjective and automated reads being blinded to each other, as well as to the gold standard consensus pathology read by 2 expert GI pathologists. The subjective reads will be compared to the automated reads and the consensus pathology reads.

Subjects at the Jilin site will be asked to complete a survey addressing barriers to esophageal cancer screenings. Subjects will be asked about beliefs and attitudes surrounding screening techniques.

Section G: Sample Size/Data Analysis

G1. Sample Size

How many subjects (or specimens, or charts) will be used in this study?

Local: 300 Worldwide: 1300

Please indicate why you chose the sample size proposed:

This is an IRB revision and will NOT change our proposed sample size. Rather, in the remaining patients to be accrued, we will determine the accuracy of our revised (AR platform). Thus, the goals and sample size of the original trial will remain intact which is to compare LCE to LCE+HRME (subjective read).

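### Enrolling 650 surveillance patients does not secure 130 benign patients: 130 is only the expected count at exactly 80% neoplasia, and the plan expects more than 80%

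*Combined protocol and SAP*

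**What the plan says.** All of this is in the combined protocol and SAP.

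- **Requirement (G1, Sample Size).** "With significance level of 0.05 and 80% power, we need 223 neoplastic patients and 65 benign patients in each arm". Over the two arms: "Hence, we need 446 neoplastic patients and 130 benign patients". The inputs are LCE sensitivity of about 95% and specificity of about 65%, against at least 90% and 85% for LCE+HRME.
- **Prevalence (G1).** From preliminary results, "greater than 80% patients in the surveillance group would have neoplasia".
- **Accrual claim (G1).** "We anticipate the enrollment of total 650 patients in the surveillance group to ensure the accrual of 446 neoplastic patients and 130 benign patients".
- **Analysis times (G2, Data Analysis).** "The analysis will be performed when 220, 440 and 650 study subjects have been accrued, respectively". The trigger is total accrual. No rule on the number of benign patients appears here or elsewhere.
- **Significance levels (G2).** The plan calls for a "two sided significance level of 0.0026 and 0.0114 for the interim analysis and 0.0464 for the final analysis".

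G1 allows 8% for loss or incomplete data in the screening group. It states no such allowance for surveillance.

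**The concern.** A statement that more than 80% have neoplasia sets a floor under the neoplastic count and a ceiling over the benign count. The plan treats it as securing both. The benign count is the binding one, and it is met only on average and only at the most favourable edge of the stated range.

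G2 makes the surveillance primary analysis a pair of tests: non-inferiority in sensitivity and superiority in specificity. The second uses benign patients only, and higher specificity is the improvement the trial expects from the device (Section D). If fewer than 130 benign patients accrue, the specificity test has less than its stated power, and a non-significant result would be read against a power the design did not have.

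**Working it through.** **Step 1. Reproduce the per-arm counts.** G1 cites a textbook formula without writing it out and does not say whether alpha is one- or two-sided. A log-ratio formula for two independent arms at one-sided 0.05 and 80% power returns both figures. It uses (1.645 + 0.842)² ≈ 6.183.

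- Specificity, with false-positive rates 0.35 and 0.15: n = 6.183 × [0.65/0.35 + 0.85/0.15] / [ln(0.15/0.35)]² = 6.183 × 7.524 / 0.718 = 64.8, so 65 (plan: 65).
- Sensitivity, 0.95 in both arms with null ratio 0.90/0.95: n = 6.183 × [2 × 0.05/0.95] / [ln(0.90/0.95)]² = 222.6, so 223 (plan: 223).

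At two-sided 0.05 the same formulas give 82.3 and 282.6, which do not match. The per-arm counts are therefore sound on this inferred basis. The problem lies in the step from 130 benign patients to 650 enrolled.

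**Step 2. Expected counts.** The two requirements total 446 + 130 = 576, which leaves 650 − 576 = 74 patients spare. At 80% neoplasia:

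- Neoplastic: 650 × 0.80 = 520, which is 520 − 446 = 74 above the requirement.
- Benign: 650 × 0.20 = 130, which is 0 above the requirement.

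The whole surplus falls on the neoplastic side.

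**Step 3. Chance of reaching 130, and power.** The benign count is taken as Binomial(650, 1 − prevalence). Specificity power for n benign patients per arm is Φ(ln(0.35/0.15) / √(7.524/n) − z), with n set to half the expected benign count and z = 1.645 for one-sided 0.05. For n = 65: 0.847/0.340 − 1.645 = 0.846, and Φ(0.846) = 0.801.

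| Neoplasia | Expected benign | P(at least 130) | Power, one-sided 0.05 |
|---|---|---|---|
| 80% | 130 | 0.516 | 80.1% |
| 81% (assumed) | 123.5 | 0.272 | 78.3% |
| 82% (assumed) | 117 | 0.102 | 76.4% |
| 85% (assumed) | 97.5 | 0.0004 | 69.6% |
| 90% (assumed) | 65 | about 0 | 54.6% |

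The chance of at least 446 neoplastic patients exceeds 0.999 in every row. A 90% chance of at least 130 benign patients needs a prevalence of about 78% or lower, outside the range the plan expects.

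**Step 4. Sensitivity to the test and to alpha.**

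- A one-sided 0.05 pooled difference-of-proportions test does not reproduce 65, since it needs 57 per arm. It gives 84.5% power at 80% neoplasia, 81.0% at 82% and 74.3% at 85%, and crosses 80% at about 82.5%.
- At G2's two-sided 0.0464 for the final analysis, the log-ratio formula gives 69%, 67%, 64%, 57% and 41% down the table. Counting the two interim looks adds less than 1 point.

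The drop of about 11 points at 80% neoplasia (80.1% to 69.1%) comes from the alpha level, not from prevalence. It is a separate inconsistency and is not counted in this point.

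**The case against.** The arithmetic on the benign count is not in dispute. The case on the other side is about size.

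- **Missing 130 by a few patients costs little.** Averaging the formula's power over the binomial benign count at 80% neoplasia gives 79.9%, against 80.1% at exactly 130. This stands: the 52%, 27% and 10% chances show that the assurance is wrong, but they do not measure lost power.
- **The planning formula is conservative.** Exact enumeration of the one-sided log-ratio test (zero counts set to 0.5) gives 84% power at 65 per arm, 80% at 58 and 74% at 49. On that basis, and on the difference-of-proportions test, 80% power survives to about 82% neoplasia. This stands too: the benign count has no margin, while the power has a little. The planning formula is still the right yardstick for the stated 80%, because it is the one that yields 65 and 223.
- **The larger losses rest on assumed prevalences.** True. The plan gives neither 85% nor 90%, nor any upper limit. The core error needs no assumption, since at exactly 80% the chance of reaching 130 is already close to one half.
- **The 0.0464 figures belong to another issue.** Largely accepted. They matter here only because a restated power must name the alpha level that will be used.
- **Enrolment will not change.** G1 says so, and the fix does not ask for it.

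**Conclusion.** The concern holds. On the plan's own figures, 650 surveillance patients give an expected 130 benign patients at 80% neoplasia and fewer at any higher prevalence. The stated 80% specificity power therefore applies only at the boundary of the range the plan expects.

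On the inferred planning formula at one-sided 0.05, the prevalence effect is 2 to 4 points at 81–82%, about 10 points at 85% and about 26 points at 90%. Less conservative calculations keep 80% power to about 82% neoplasia. The count result depends on no formula. The power figures depend on the inferred formula, one-sided alpha, equal arms and assumed prevalences. The neoplastic count and the sensitivity test are not affected.

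This should be corrected, with high confidence in the count arithmetic and less in any single power figure.

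**What to change.** 1. In G1, replace the assurance with expected counts. For example: *We will enrol 650 surveillance patients. At 80% neoplasia this gives an expected 520 neoplastic and 130 benign patients; at higher prevalence fewer benign patients are expected.* This can be done at once.
2. Add a short table of specificity power at labelled prevalences (for example 80%, 82%, 85% and 90%), naming the formula and the alpha level. Use the level the final analysis will apply, so G1's 0.05 and G2's two-sided 0.0464 have to be reconciled before the table is written.
3. Optional: since G1 indicates that accrual is under way, report the benign count to date, pooled over both arms and for description only, in place of assumed prevalences. Any rows for incomplete data should be labelled as an assumption.

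The cost is a sentence and a small table. Enrolment, the primary test, the surveillance-only population and the interim schedule stay unchanged. The downside is a less favourable stated power for specificity.

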In a single arm, NIH-funded pilot trial in the United States and China, we were able to obtain a sensitivity and specificity of 100 and 79% when the HRME was used in conjunction with Lugol's chromoendoscopy in high-risk subjects undergoing endoscopic screening or surveillance. The negative predictive value of the HRME was 97% which suggests that use of the HRME may significantly decrease the number of mucosal biopsies needed during endoscopic evaluation. Given Lugol's known high sensitivity but low specificity (95% and < 60%) this is promising as the HRME may significantly reduce the false positive rate of Lugol's chromoendoscopic screening, the current standard of care. Research subjects recruited at the Jilin site will also be asked to complete a brief survey about beliefs and attitudes about esophageal cancer and screening. It is important to understand factors affecting patient decisions about cancer screening to increase utilization of new technologies and ultimately improve early detection of esophageal cancer in this high-risk population.

Section D: Purpose and Objectives

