The overall objective of this multicenter trial is to determine whether use of a low-cost, high-resolution microendoscope during diagnostic upper endoscopy can improve the efficiency and accuracy of endoscopic screening for esophageal squamous cell neoplasia (ESCN). This is a trial of a novel technology, a miniaturized, low cost (<\$3,500) microscope device which can be used during upper endoscopy to image the gastrointestinal epithelium. This portable, battery-operated high-resolution microendoscope (HRME) was developed by our collaborators at Rice University and provides greater than 1000X magnified images of the esophageal mucosa. In a single-arm, pilot study of the device in an enriched population of 60 high-risk subjects in China and the US, we used the microendoscope during routine Lugol's chromoendoscopic screening to categorize areas of abnormality (unstained areas). The sensitivity /specificity for the device seen in this study were 100% and 79%-a significant improvement over the sensitivity/specificity of Lugol's chromoendoscopy which were 97% and 52%. Thus, our presumption is that HRME can enhance the specificity (and lower the false positive rate) of Lugol's. As part of a National Cancer Institute R01 supplement (Figure 1), we have enhanced the current HRME technology by introducing an automated, ergonomic, augmented reality platform. The augmented reality platform displays, in real-time, the microscopic image colocalized with the endoscopic image, potentially allowing more targeted biopsies/treatment and increased accuracy. Our central hypothesis is that our approach can improve the efficiency and clinical impact of endoscopic screening and surveillance of ESCN by providing *in-vivo* optical biopsies comparable to standard histology. Specifically, HRME will facilitate accurate, rapid real-time endoscopic screening by non-expert clinicians. We also hypothesize the HRME will provide additional, more accurate information regarding the presence of neoplasia that will impact upon the physician's decision to obtain a mucosal biopsy or perform endoscopic therapy (endoscopic mucosal resection or ablation). This could potentially minimize the number of unnecessary biopsies and enable the physician to perform endoscopic therapy at the time of the initial examination, rather than delaying endoscopic treatment to another procedure following pathologic confirmation of the initial biopsies. We will compare (1) the current endoscopic "standard of care" (white light endoscopy with Lugol's iodine), (2) HRME with subjective, human interpretation, and (3) augmented reality HRME (software, 'machine' interpretation). The addition of (3) is the basis for our revision R01 and this amended IRB. The accuracy, efficiency, clinical impact and cost-effectiveness of each approach in the diagnosis and management of ESCN will be determined in both the Chinese and US healthcare systems. Specific endpoints: 1. Efficiency: (a) Diagnostic Yield: The number of neoplastic biopsies/total number of biopsies obtained in patients who receive biopsies. (b) 'Patients saved': Number of patients who receive no biopsies (c) Procedure time: Total procedure time in each group 2. Clinical impact: Determine potential clinical impact of HRME by determining if use of the device (with both subjective and automated read) changes the decision to perform endoscopic therapy and perform, or not perform, a mucosal biopsy when compared to LC alone. 3. Prospectively compare the performance characteristics of HRME-LC to LC for the prediction of squamous esophageal neoplasia in flat mucosa and mucosal lesions using histopathology as the gold standard. (a) Determine the sensitivity, specificity, positive and negative predictive value for the identification of neoplasia on a per biopsy and per patient analysis. 4. Determine the cost-effectiveness of HRME-LC to LC alone for the endoscopic screening and surveillance of ESCN in the US and China.

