In both groups, per standard of care, endoscopic examination will be performed using white-light endoscopy with Lugol's dye-spray. In each subject, the location of each unstained area (level, quadrant) will be recorded and digital images obtained. The endoscopist's clinical impression will be recorded for each Lugol's abnormal area and visible lesion ('nonneoplastic' vs. 'neoplastic') as well as his/her proposed plan: a. no biopsy, b. biopsy, c. endoscopic treatment/removal. In the standard-of-care arm (Group B), biopsies will be obtained of all Lugol's abnormal areas. Likewise, Group A will receive the clinician subjective HRME read + augmented reality software HRME read, sequentially, of all Lugol's unstained (abnormal) areas prior to tissue biopsy. For imaging, 1-10 ml proflavine hemisulfate (0.01%) will be sprayed on the esophageal mucosa. The HRME probe placed gently on the mucosa and the augmented reality microscopic (HRME) image displayed on the glasses, with the endoscopic image (monitor) behind it. The endoscopist will first make a subjective interpretation (neoplasia vs. no neoplasia) and plan of action (biopsy, no biopsy, treat) WITHOUT the image-analysis software. Once this qualitative ("Human") read is recorded, the image analysis software will be turned on and the software diagnosis provided in real-time. This quantitative ("Machine") read and the revised plan of action will be recorded. The HRME procedure (including Human and Machine reads) as well as standard endoscopy and biopsy time will be recorded. The research coordinators will indicate the biopsy number/location on an esophageal map diagram. The biopsies from each site will be placed in formalin per standard of care and labeled according to biopsy location (quadrant: 12, 3, 6, 9 o'clock). In all subjects, all Lugol's abnormal areas will be biopsied (to uphold the standard of care, per IRB); however, HRME "non-neoplastic" sites will be considered not tissue-biopsied for purpose of the analysis. All biopsies will be submitted for consensus diagnosis by 2 expert GI pathologists.

A schematic of the existing trial with the proposed revision is shown in Figure 2. The IRB revision is shown in RED. We anticipate that this revision will add an additional 30-60 seconds per procedure but will otherwise not change patient care.

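### Screening NPV target of 99% and its 82.1% power do not follow from a design that reads HRME only on Lugol's-unstained areas, unless a negative LCE is defined differently

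*Combined protocol and SAP*

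**What the plan says.** All references are to the Combined protocol and SAP.

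- **G1, screening group.** The baseline is "The NPV for using LCE alone is about 95" percent, and the target is "We hypothesize that the NPV for LCE+HRME should be at least 99% to be useful". On power: "A sample of 300 per arm would provide 82.1% power for this hypothesis with a 5% type-I error". On recruitment: "Assuming an 8% loss to follow-up or incomplete data, we need to recruit 325 subjects per arm in the screening population".
- **G2.** The primary goal in screening is to show a higher NPV with LCE+HRME than with LCE alone. On the test: "This is done using Fisher's exact test".
- **F2.** Group A receives the HRME reads "sequentially, of all Lugol's unstained (abnormal) areas prior to tissue biopsy". Every Lugol's-abnormal area is biopsied in both arms, but an HRME-negative site is analysed as if it had not been biopsied. No HRME read or biopsy of normally stained mucosa is described. Before HRME, the endoscopist also records an impression (non-neoplastic or neoplastic) for each abnormal area and visible lesion.
- **Section D.** The expected benefit is in specificity: "our presumption is that HRME can enhance the specificity (and lower the false positive rate) of Lugol's".
- **Preliminary studies.** From the pilot: "The negative predictive value of the HRME was 97" percent.

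No section defines a negative LCE patient for NPV. None gives sensitivity, specificity or prevalence for the screening group.

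**The concern.** A second read confined to areas that the first test has already flagged forms a serial test. It can change a positive to a negative but not the reverse. If a patient without unstained areas counts as LCE-negative, every neoplasm that Lugol's misses is also missed by LCE+HRME, and HRME may add misses. The gain is then in specificity, as Section D says, and NPV benefits only indirectly.

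The primary hypothesis for 650 of the 1,300 patients nevertheless needs NPV to rise from 95% to 99%. If the design cannot produce that rise, a device that clears every Lugol's false positive and loses no neoplasia would still miss the stated usefulness bar and would probably give a non-significant primary result. Readers could conclude that HRME is of no use in screening when the target was at fault.

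**Working it through.** **Inputs.** From G1, screening: NPV 95% and 99%, 300 per arm, 5% type-I error. From G1, surveillance: LCE sensitivity/specificity 95%/65%, LCE+HRME at least 90%/85%. From the Section D pilot: Lugol's 97%/52%, HRME 100%/79%. Using the surveillance and pilot figures for screening is an assumption.

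**1. The plan's power.** Two-sided pooled z-test, 300 per arm, 95% vs 99%:
- mean proportion 0.97; null SE = √(2 × 0.97 × 0.03/300) = 0.01393
- alternative SE = √((0.95 × 0.05 + 0.99 × 0.01)/300) = 0.01383
- z = (0.04 − 1.96 × 0.01393)/0.01383 = 0.918, so power is 82.07%

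This reproduces the stated 82.1%. Fisher's exact test, two-sided, gives 79.8% for the same inputs.

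**2. Ceiling if a negative LCE means no unstained area.** NPV odds = TN/FN, which is 19 at 95% and 99 at 99%. FN cannot fall. A perfect HRME raises TN by the factor 1/spec, where spec is Lugol's specificity, so the highest NPV is (19/spec)/(1 + 19/spec). Prevalence cancels.

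| Lugol's specificity | Highest NPV |
|---|---|
| 65% | 96.7% |
| 60% | 96.9% |
| 52% | 97.3% |

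Reaching 99% needs spec ≤ 19/99 = 19.2%. With HRME specificity 85% and no neoplasia lost, the odds are 19 × 0.85/0.65 = 24.8, an NPV of 96.1%.

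**3. Power at that ceiling, 300 per arm against 95%.**

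| NPV with LCE+HRME | Pooled z | Fisher's exact |
|---|---|---|
| 96.7% | 17.8% | 13.3% |
| 97.3% | 31.9% | 25.5% |

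**4. If a negative LCE means an abnormal area judged non-neoplastic.** HRME can now correct a miss. At fixed prevalence, NPV odds are proportional to spec/(1 − sens).
- LCE: 0.65/0.05 = 13.
- Moving the odds from 19 to 99 needs 13 × 99/19 = 67.7. At specificity 85%, 1 − sens = 0.85/67.7 = 0.0126, so sensitivity must be about 98.7%.
- At the plan's 90%/85% the ratio is 0.85/0.10 = 8.5, below 13, so NPV falls. Sensitivity 95%, specificity 65% and NPV 95% together imply a prevalence of 40.6%; there NPV goes from 95.0% to 92.6%.

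**5. Denominator.** NPV is a proportion of test-negative patients, not of all 300. At prevalence 40.6%:
- LCE: 300 × (0.65 × 0.594 + 0.05 × 0.406) ≈ 122
- LCE+HRME at specificity 85%, sensitivity held at 95%: 300 × (0.85 × 0.594 + 0.05 × 0.406) ≈ 158

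With 122 and 158 negatives, two-sided Fisher power even for 95% vs 99% is about 50%.

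**The case against.** **The definition is open, so 99% is not shown to be impossible.** A reader might infer that the target is out of reach whatever happens. The documents do not support that. F2 records an impression for each abnormal area before HRME, and on that reading HRME can correct LCE misses. The pilot fits this reading better: HRME sensitivity was 100% against 97% for Lugol's, and a strictly serial test in the same subjects cannot exceed its first stage. It is also the only reading on which LCE negatives have index histology. This objection stands and makes the conclusion conditional. On the other side, F2 biopsies every unstained area in Group B, and G2 describes patients spared biopsy as Lugol's-positive and HRME-negative. Both favour the unstained-area reading.

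**NPV can rise with false negatives unchanged.** A reader might also infer that HRME cannot raise NPV at all. That is wrong, because added true negatives raise it. The ceiling calculation is therefore needed, and it borrows Lugol's specificity from surveillance or from an enriched pilot. The conclusion would change only at 19% or lower, far below the 52% to 65% point values in the documents.

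**The 95% baseline may not hold.** At assumed prevalences of 5% and 10%, Lugol's at 95%/65% already has NPV 99.6% and 99.2%. The 99% bar could then be met, but almost no room is left for superiority. The fall to 92.6% belongs to 40.6% prevalence, and 90% is the plan's floor for sensitivity, not its expected value.

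**Conclusion.** The target and the power need correction; confidence is moderate because the size depends on an undefined term.

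- **Negative LCE = no unstained area.** The ceiling from a 95% baseline is about 96.7% to 97.3%, assuming Lugol's specificity of 65% to 52%. The 82.1% is then power for an effect that the design does not produce.
- **Negative LCE = abnormal area judged non-neoplastic.** 99% is attainable, but only with sensitivity near 98.7% at specificity 85%. The pilot's 100% would meet this; the planned floor of 90% would not. The pilot's reported HRME NPV of 97% is itself below the bar.

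On either reading, 95%/65% against 90%/85% lowers NPV, and the power calculation uses all patients where only test-negatives count.

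**What to change.** In G1 and G2:

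1. Define a negative LCE and a negative LCE+HRME per patient, and say how negatives are verified. If patients with no unstained area are simply counted as disease-free, observed LCE NPV is 100% under that definition and superiority is impossible. The follow-up at years 1, 3 and 5 in F2 is described for progression, not for this purpose.
2. Replace 99% with a value reachable under the chosen definition, and state the screening sensitivity, specificity and prevalence behind it and behind the 95% baseline.
3. Restate power on the expected number of test-negatives, using Fisher's exact test and stating whether it is one- or two-sided.

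The sponsor may consider carrying the surveillance pair into screening: superiority in specificity together with non-inferiority in sensitivity, with NPV and its 95% CI in support. That changes the primary endpoint, is a trade-off, and needs its own power calculation. Superiority in specificity must not stand alone: a serial test can only raise specificity, so a device that called everything negative would win.

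The three changes are an amendment to the protocol and SAP text. Defining and restating add no procedures, although the chosen method of verifying negatives might. The price is that the stated power becomes much less favourable at the present sample size.
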